3.17 Rescreening

Subjects who initially screen fail for the study may be permitted to re-screen following re-consent. The subject must meet all the eligibility criteria as assessable at the time of re-screening to qualify for the study. There is no minimum period of time a subject must wait to re-screen for the study.

If the subject had a complete initial screening evaluation including the TB test, Hepatitis B virus (HBV), Hepatitis C virus (HCV), human immunodeficiency virus (HIV), electrocardiogram (ECG), and chest x-ray these tests will not be required to be repeated for re-screening provided the conditions noted in Section 3 are met and no more than 90 days have passed.

If a subject is being rescreened \leq 14 days from the date of the previous screening testing, it is not required to repeat testing for chemistry/hematology, urinalysis, serum pregnancy, and C. difficile provided that the subject's health status has not changed to warrant a repeat test. If a subject is being rescreened more than 14 days (> 14 days have passed) from the collection date of the previous screening laboratory testing then chemistry/hematology, urinalysis, serum pregnancy, and C. difficile should be repeated during rescreening.

[figure not shown]
An endoscopy with biopsy will not be required to be repeated for re-screening provided the conditions noted in Section 3.16 are met and the endoscopy is within 45 days of the Baseline visit. All other screening procedures will be repeated unless otherwise stated above. Sites may contact the AbbVie TA MD if there are questions on if subjects should or should not be re-screened.

All subjects need to have their average daily Stool Frequency subscore, average daily RBS, and Adapted Mayo score calculated to verify eligibility criteria before randomization at Baseline.

4 SAFETY MANUAL

4.1 Methods and Timing of Safety Assessment

All serious and nonserious adverse events that could be related to study procedures will be collected from the time the subject signed the study-specific informed consent until study drug administration. From the time of study drug administration until 30 days after the last dose of study drug or study treatment, all nonserious and serious adverse events will be collected whether solicited or spontaneously reported by the subject. After 30 days following the last dose of study drug or completion of study treatment only spontaneously reported SAEs will be collected (nonserious AEs will not be collected).

4.2 Reporting Adverse Events and Intercurrent Illnesses

In the event of an SAE, whether associated with study drug or not, the investigator will notify Clinical Pharmacovigilance within 24 hours of the site being made aware of the SAE by entering the SAE data into the electronic data capture (EDC) system. SAEs that occur prior to the site having access to the RAVE® system, or if RAVE is not operable, should be documented on the SAE nonCRF forms and emailed (preferred route) or faxed to Clinical Pharmacovigilance within 24 hours of the site being made aware of the SAE.

Email: [contact]

FAX to: [contact]

For safety concerns, contact the Immunology Safety Team at:

Immunology Safety Team
[name]
[name]
Toll Free: [contact]
Email: [contact]

For any subject safety concerns, please contact the physician listed below:

PPD

EMERGENCY MEDICAL CONTACT:

[name]

AbbVie

**[name]
[name]**

Contact Information:

Office: PPD

Mobile:

Email:

In emergency situations involving study subjects when the primary Therapeutic Area Medical Director is not available by phone, please contact the 24-hour AbbVie Medical Escalation Hotline where your call will be re-directed to a designated backup AbbVie Therapeutic Area Medical Director:

[contact]

The sponsor will be responsible for Suspected Unexpected Serious Adverse Reactions (SUSAR) reporting for the Investigational Medicinal Product (IMP) in accordance with Directive 2001/20/EC.

State of Emergency or Pandemic-Related Acceptable Protocol Modifications

Supplemental study case report forms should be completed in the event of COVID-19-related missed/virtual visits, study drug interruptions or discontinuations, vaccines, or adverse events (including capture of specific signs/symptoms of infection and testing results).

SARS-CoV-2 infections should be captured as adverse events. If the event meets the criteria for a serious adverse event (SAE), then follow the SAE reporting directions per the protocol and above. The following COVID-19-related supplemental eCRFs should be completed (for both serious and nonserious events):

- COVID-19 Supplemental Signs/Symptoms
- COVID-19 Status Form

If a subject has a confirmed or suspected SARS-CoV-2 infection and study drug was interrupted, the investigator should contact the sponsor emergency medical contact listed above before reintroducing study drug.

Reactions known to be associated with the SARS-CoV-2 vaccine should be reported as adverse events. If the event meets the criteria for an SAE, then follow the SAE reporting directions. All adverse events associated with the SARS-CoV-2 vaccine will be linked to the vaccine on the COVID-19 Vaccine eCRF.

5 COUNTRY-SPECIFIC REQUIREMENTS

5.1 SUSAR Reporting

AbbVie will be responsible for Suspected Unexpected Serious Adverse Reactions (SUSAR) reporting for the Investigational Medicinal Product (IMP) in accordance with global and local guidelines and Appendix A of the Investigator Brochure will serve as the Reference Safety Information (RSI). The RSI in effect at the start of a DSUR reporting period serves as the RSI during the reporting period. For follow-up reports, the RSI in place at the time of occurrence of the 'suspected' Serious Adverse Reaction will be used to assess expectedness.

6 STUDY DRUG

6.1 Treatments Administered

The study drug (ABBV-668) will be dispensed in the form of capsules at the visits listed in Section 2.1. Subjects will be instructed to take study drug at the same time every day with or without food.

ABBV-668 will be provided by AbbVie as CCI [REDACTED] to be taken as CCI mg PO BID CCI [REDACTED]

Study drug administration instructions will be provided separately.

Study drug must not be dispensed without contacting the IRT system. Study drug may only be dispensed to subjects enrolled in the study through the IRT system. At the end of the Treatment Period or at the Premature D/C visit, the site will contact the IRT system to provide visit date information and study drug return information for each kit.

6.2 Packaging and Labeling

All study drugs will be supplied in bottles.

Each bottle will be labeled as required per country requirements.

The labels must remain affixed to the bottles. All blank spaces should be completed by site staff prior to dispensing to subject.

6.3 Storage and Disposition of Study Drug

Study drug must be stored between 2°C to 25°C (36°F to 77°F).

The investigational product is for investigational use only and are to be used only within the context of this study. The study drug supplied for this study must be maintained under adequate security and stored under the conditions specified on the label until dispensed for subject use or destroyed on site as appropriate.

Sites are responsible for maintaining the investigational study drug according to the storage conditions specified on the clinical label and monitoring for temperature excursions with the use of a calibrated continuous temperature monitoring device (for example, chart recorders and/or acceptable calibrated min/max thermometers) or continuous monitoring systems. Specific guidance on appropriate temperature monitoring and temperature excursions reporting requirements will be provided separately.

6.4 Method of Assigning Subjects to Treatment Groups

This is a non-randomized, open-label, single arm study. All eligible subjects will receive the same dosage of ABBV-668 for 16 weeks.

At the screening visit, all subjects will be assigned a unique subject number using the IRT. For subjects who do not meet the study selection criteria, the site personnel must contact the IRT system and identify the subject as a screen failure.

Subjects who are enrolled will retain their subject number assigned at the screening visit throughout the study. Upon receipt of study drug, the site will acknowledge receipt in the IRT system.

Contact information and user guidelines for IRT use will be provided to each site.

6.5 Selection and Timing of Dose for Each Subject

CCI [REDACTED] of ABBV-668 will be dosed together BID. All subjects should take all doses of study drug with or without food around the same time each day.

7 References

1. Food and Drug Administration. Ulcerative Colitis: Developing Drugs for Treatment Guidance for Industry. 2022.

8 Appendices

8.1 SCREENING/ANNUAL TB RISK ASSESSMENT QUESTIONNAIRE EXAMPLE

For screening TB risk assessment, ask Part I and Part II questions.

Part I

Has an immediate family member or other close contact been newly diagnosed with or treated for active or latent tuberculosis during the last 3 months?

Within the past year, have you, or an immediate family member, had any of the following problems lasting for 3 weeks or longer which remained unexplained:

- Chronic Cough
- Production of Sputum
- Blood-Streaked Sputum
- Weight Loss
- Fever
- Fatigue/Tiredness
- Night Sweats
- Shortness of Breath

(reference: <https://www.cdc.gov/tb/topic/testing/diagnosingltbi.htm>)

Part II

Have you ever been diagnosed or treated for active or latent tuberculosis?

Have you lived in or had prolonged travels to a TB endemic region?

(reference: http://gamapserver.who.int/gho/interactive_charts/tb/cases/atlas.html)

Have you lived or worked in a prison, refugee camp, homeless shelter, immigration center, or nursing home?

8.2 Mayo Score

Three different Mayo Score are evaluated in this protocol:

- Full Mayo Score
- Adapted Mayo Score
- Partial Adapted Mayo Score

The Full Mayo Score is a composite of the following subscores: Stool Frequency subscore, Rectal Bleeding subscore, Endoscopy subscore, and Physician's Global Assessment subscore.

The adapted Mayo Score is a composite of the following subscores: Stool Frequency subscore, Rectal Bleeding subscore and Endoscopy subscore.

The Partial Adapted Mayo Score is a composite of the following subscores: Stool Frequency subscore and Rectal Bleeding subscore.

Adapted Mayo Score (also known as Modified Mayo Score):¹⁻³

Stool Frequency	
0	Normal number of stools for this patient
1	1-2 more stools than normal
2	3-4 more stools than normal
3	5 or more stools more than normal
Rectal Bleeding	
0	No blood seen
1	Stool with streaks of blood
2	Stool with more than streaks of blood
3	Blood alone passed
Endoscopy	
0	Normal appearance mucosa
1	Mild disease (erythema, decreased vascular pattern), no friability
2	Moderate disease (marked erythema, absent vascular pattern, friability, erosions)
3	Severe disease (spontaneous bleeding, ulcerations)

Stool Frequency Subscore

- The subject should be asked to identify at the screening visit how many bowel movements (when a subject passed stool, blood alone, blood and mucus, or mucus only) he or she had in a

24-hour period when their ulcerative colitis is **not** active. This value will serve as the reference Stool Frequency and must be a full number of at least 1.

- The Stool Frequency subscore is calculated by comparing the stool frequency to the reference Stool Frequency.
- Subjects will record the daily number of bowel movements throughout the trial. Using these numbers, the Stool Frequency subscore will be assessed for each study day as follows:
 - A number of bowel movements lower than or equal to the reference number of bowel movements should be scored as 0 = Normal.
 - One or 2 bowel movements more than the reference number of bowel movements should be scored as 1.
 - Three or 4 bowel movements more than the reference number of bowel movements should be scored as 2.
 - Five or more bowel movements more than the reference number of bowel movements should be scored as 3.
- The Stool Frequency subscore during days which the subject received anti-diarrheal medication will be scored as a 3.
- The Stool Frequency subscores based on 7 days prior to each study visit will be averaged and used for the Stool Frequency subscore for each study visit
- A minimum of 3 consecutive days of completed diary entries or 4 nonconsecutive days are necessary. Otherwise, the Stool Frequency subscore should be considered missing.
- For visits that have endoscopies, the calculation of the 7-day average should exclude the subscores from non-applicable days which are defined as: 1) the day of bowel preparation; 2) day of endoscopy; and 3) 2 days after endoscopy. Earlier diary entries will be used accordingly to provide the most recent data for 7 applicable days prior to the respective study visit.

Rectal Bleeding Subscore

- Subjects will be assigned a daily Rectal Bleeding subscore value as follows:
 - No visible blood with stool during the respective day should be scored as 0.
 - Stool with streaks of blood during the respective day should be scored as 1.
 - Stool with more than streaks of blood during the respective day should be scored as 2.
 - Blood alone passed during the respective day should be scored as a 3.
- The Rectal Bleeding subscores based on 7 days prior to each study visit will be averaged and used for the Rectal Bleeding subscore for each study visit.
- A minimum of 3 consecutive days of completed diary entries or 4 nonconsecutive days are necessary. Otherwise, the Rectal Bleeding subscore should be considered missing.
- For visits that have endoscopies, the calculation of the 7-day average should exclude the subscores from non-applicable days, which are defined as: 1) the day of bowel preparation,

2) day of endoscopy, and 3) 2 days after endoscopy. Earlier diary entries will be used accordingly to provide the most recent data for 7 applicable days prior to the respective study visit.

Endoscopy Subscore

- The endoscopist should evaluate each observed segment of the colon (rectum, sigmoid, descending colon, transverse colon, ascending colon/cecum) by using the classification as follows:
 - 0 = Normal appearance of mucosa
 - 1 = Mild disease (erythema, decreased vascular pattern), no friability
 - 2 = Moderate disease (marked erythema, absent vascular pattern, friability, erosions)
 - 3 = Severe disease (spontaneous bleeding, ulcerations)
- The endoscopic subscore for the subject will be the worst score of the observed segments.
- The local endoscopist should also separately assess presence or absence of friability (yes/no).
- The endoscopy will be recorded (not a still image) and sent to a central review vendor for scoring as described in the central review charter.

Physician's Global Assessment Subscore

The physician's global assessment acknowledges the 2 subject-reported subscores, the endoscopy subscore as applicable, and the subject's daily record of abdominal pain based on the 7 days prior to the visit, and other observations such as physical findings, and the subject's performance status in order to assess disease activity as follows:

0 = Normal

1 = Mild disease

2 = Moderate disease

3 = Severe disease

Document Approval

Study Protocol - m21446-protocol-v2-0-ops-manual-text - 03-Mar-2023

Version: 1.0 **Date:** 03-Mar-2023

Company ID: 20230303-0900f9f6860b00d2-1.0-en

Signed by:	Date:	Meaning of Signature:
PPD	03-Mar-2023 17:11 UTC	Approver
	03-Mar-2023 15:58 UTC	Approver
	03-Mar-2023 15:54 UTC	Approver - Statistics

Document Approval

Study Protocol - m21446-protocol-v2-0-text - 03-Mar-2023

Version: 1.0 **Date:** 03-Mar-2023

Company ID: 20230303-0900f9f6860b00d0-1.0-en

Signed by:	Date:	Meaning of Signature:
PPD	03-Mar-2023 17:12 UTC	Approver
	03-Mar-2023 15:58 UTC	Approver
	03-Mar-2023 15:54 UTC	Approver - Statistics

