5 STUDY ACTIVITIES

5.1 Eligibility Criteria

Subjects must meet all of the following criteria to be included in the study. Anything other than a positive response to the questions below will result in exclusion from study participation.

Consent

- 1. Subject must voluntarily **sign and date an informed consent**, approved by an independent ethics committee (IEC)/institutional review board (IRB), prior to the initiation of any screening or study-specific procedures.

Demographic and Laboratory Assessments

- 2. Adult **male or female**, at least 18 years old at time of the baseline visit.
- 3. **Laboratory values** meeting the following criteria within the screening period prior to the first dose of study drug:
 - Hemoglobin \geq 8 g/dL;
 - Serum aspartate transaminase (AST) and alanine transaminase (ALT) $\leq 2 \times$ upper limit of normal (ULN).
- 4. Are willing and able to comply with procedures required in this protocol.

- ✓ 5. Estimated glomerular filtration rate (eGFR) calculated by Cockcroft-Gault ≥ 90 mL/min at the Screening visit.

Disease/Condition Activity

- ✓ 6. Diagnosis of UC for at least 90 days prior to Baseline. Appropriate documentation of biopsy results consistent with the diagnosis of UC in the assessment of the investigator, must be available prior to enrollment.
- ✓ 7. Subject meets the following disease activity criteria: Active UC with an Adapted Mayo score of 5 to 9 points and ESS of 2 to 3 (confirmed by central review prior to enrollment).

Subject History

- ✓ 8. Subject must not have an active, chronic, or recurrent infection that based on the investigator's clinical assessment makes the subject an unsuitable candidate for the study, or the following:
 - Subject must not currently be positive with *C. difficile* toxin as identified during Screening or another known intestinal pathogen;
 - Subject must not be infected with human immunodeficiency virus (HIV);
 - Subject must not have active hepatitis B or hepatitis C (as defined in the Operations Manual);
 - Subject must not have evidence of active tuberculosis (TB) or meet TB exclusionary parameters (See specific requirements for TB testing in Section 3.13 of the Operations Manual).

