3.16 Additional Assessments as Required

Endoscopy

Endoscopy at/during Screening will be required to calculate the Mayo endoscopy subscore (confirmed by a central reader) at Baseline. Endoscopic evaluations using Mayo endoscopic score confirmed by central reader will be done at Screening, Week 8 and Week 16.

The same endoscopist, where possible, should perform all endoscopies. In addition, where possible, the investigator or sub-investigator should be the endoscopist for the study. It is expected that all subjects who remain in the study through at least Week 6 will have a Week 8 endoscopy.

A full colonoscopy will be performed at Screening unless the subject underwent a full colonoscopy within 12 months prior to Screening. There must be appropriate documentation available to confirm the diagnosis, extent of disease, and to exclude dysplasia and colon cancer. If this is available, the screening endoscopy may be either a full colonoscopy or a flexible sigmoidoscopy. All other endoscopies may be flexible sigmoidoscopies or colonoscopies at the discretion of the investigator.

All endoscopies will be performed and recorded at the site in a video format. Videos from subjects with eligible Mayo endoscopic subscores during Screening and all videos from subjects at Week 8 and Week 16 will be sent to a central review vendor and scored as described in the central review charter. Endoscopies will be evaluated using the Mayo endoscopic subscore. The Mayo endoscopic subscore, including the presence or absence of friability will be documented by the endoscopist at the site and maintained in the subject's source documents. If, in the assessment of the site endoscopist, the Screening endoscopy does not indicate an endoscopy subscore of 2 or 3 or the extent of inflammation is

limited to the rectum, per eligibility requirements, the subject should be screen-failed and the video should not be sent for central reading.

There will be a window of \pm 7 days to conduct the endoscopy. This window may be extended as necessary after consultation with the AbbVie TA MD in case of external, not subject-related circumstances (e.g., scheduling conflict).

Intestinal Biopsy

Mandatory biopsies will be collected during endoscopies occurring during Screening, Week 8, and Week 16 as described below:

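### As worded, the rule removing bowel-preparation and endoscopy days from the diary averages does not reach Baseline, so a Screening endoscopy close to Day 1 can raise the entry score and the reference for clinical response

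*Protocol*

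**What the plan says.** Operations Manual 8.2 sets the averaging period: "The Stool Frequency subscores based on 7 days prior to each study visit will be averaged". RBS is handled the same way. On missing entries it says: "A minimum of 3 consecutive days of completed diary entries or 4 nonconsecutive days are necessary". It then adds, once for each subscore: "For visits that have endoscopies, the calculation of the 7-day average should exclude the subscores from non-applicable days". Those days are the day of bowel preparation, the day of endoscopy and the 2 days after it. Earlier entries are used to make up 7 applicable days.

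Operations Manual 3.16 fixes when endoscopies occur: "Endoscopic evaluations using Mayo endoscopic score confirmed by central reader will be done at Screening, Week 8 and Week 16". The Baseline lists in Operations Manual 2.1 and Protocol Appendix D contain the Full, Adapted and Partial Mayo scores but no endoscopy. The Baseline endoscopic subscore (ESS) is carried over from Screening: "Endoscopy at/during Screening will be required to calculate the Mayo endoscopy subscore (confirmed by a central reader) at Baseline".

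Protocol 5.1, criterion 7, requires "Active UC with an Adapted Mayo score of 5 to 9 points and ESS of 2 to 3", with central confirmation before enrollment. Operations Manual 3.17 says that all subjects need their diary averages and "Adapted Mayo score calculated to verify eligibility criteria before randomization at Baseline". The only limits on the interval from Screening endoscopy to Baseline are upper ones: a 30-day screening period, and 45 days when an endoscopy is reused at rescreening.

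SAP 7.1 defines Baseline as the last non-missing value before first dose. The SAP has no rule on excluding diary days.

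**The concern.** The plan itself treats these four days as unfit for scoring, presumably because preparation raises stool counts and endoscopy with biopsies (8 per endoscopy, Screening included) can cause visible blood. That reasoning applies equally before treatment. If the exclusion operates at Week 8 but not at Baseline, the two ends of a change score are built by different rules, and the difference tends to enlarge the apparent fall.

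Two things are at stake. A subject whose symptoms put the Adapted Mayo score below 5 could be enrolled. And two secondary endpoints, clinical response per Adapted Mayo and per Partial Adapted Mayo, are defined by change from Baseline, so a raised Baseline can turn a non-response into a response.

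**Working it through.** The plan gives no figure for this rule, so there is none to reproduce. The daily scores below are assumptions.

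**1. Which endoscopy dates matter.** The Baseline window is Day -7 to Day -1. With preparation assumed on the day before, an endoscopy on day *e* affects days *e*-1, *e*, *e*+1 and *e*+2.

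| Endoscopy day | Affected days in window |
|---|---|
| -10 or earlier | 0 |
| -9 | 1 |
| -8 | 2 |
| -7 | 3 |
| -6 to -3 | 4 |
| -2 | 3 |
| -1 | 2 |

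**2. Size of the shift.** With a full diary and *k* affected days, the average is ((7-*k*) × clean score + *k* × affected score)/7. The shift per subscore is *k* × excess/7.

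**3. Entry.** Take clean SFS 1, RBS 1 and ESS 2: total 4.00, ineligible. Let affected days score SFS 3 and RBS 2. Each adds (2+1)/7 = 0.43.

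- *k* = 2: 11/7 + 9/7 + 2 = 4.86, still ineligible.
- *k* = 3: 13/7 + 10/7 + 2 = 5.29, eligible.
- *k* = 4: 15/7 + 11/7 + 2 = 5.71, eligible.

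If only stool frequency is affected, *k* = 3 gives 4.86 and *k* = 4 gives 5.14.

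**4. Partial Adapted Mayo response without change.** The *k* = 3 subject has a Baseline Partial Adapted score of 23/7 = 3.29. If symptoms are unchanged at Week 8, where the days are removed, the score is 2.00. The fall is 1.29 points, or 1.29/3.29 = 39%, with RBS 1. This meets the definition (at least 1 point and 30%, with RBS no more than 1).

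**5. Adapted Mayo response.** Take clean SFS 2, RBS 1 and ESS 2: total 5.00. Two affected days at SFS 3 and RBS 2 give 16/7 + 9/7 + 2 = 5.57. A Week 8 score of 3.50 is then a fall of 2.07 (37%), a response if the RBS condition is met. The true fall is 1.50 (30%), which misses the 2-point requirement. A full 7-day diary moves in sevenths, so 3.50 needs a shorter diary. The nearest full-diary values behave the same way: 3.43 gives 15/7 = 2.14 (38%) against a true 1.57, and 3.57 gives 14/7 = 2.00 (36%) against a true 1.43.

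**6. What one or two such subjects could do.** One misclassified subject in 40 is 2.5 percentage points. SAP Table D-1 pools placebo clinical response per Adapted Mayo as (42+44)/(154+174) = 86/328 = 26.2%, matching the stated 26% and the mean of Beta(85.7, 241.0). With the Beta(0.5, 0.5) prior and 40 subjects, 14 responders give a posterior probability of a positive difference of 0.88, and 15 give 0.93. So 15 are needed to pass 90%, the level used in the sample-size section and borrowed here because the SAP sets none for secondary endpoints. At a true rate of 26.2%, the chance of 15 or more is 7.8%. Adding 2.5 points makes it 14.7%, and adding 5 points 24.3%. This applies only if the external rates are free of the same inflation.

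**7. Week 10.** The manual allows latitude on timing: "There will be a window of \pm 7 days to conduct the endoscopy". An endoscopy 7 days after the nominal Week 8 date falls 7 days before nominal Week 10, leaving 3 affected days in that average (same geometry as Day -7 above). These raise a post-treatment score, so they work against response.

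**The case against.** The best reply is that Baseline was meant to be covered. Its Adapted Mayo score uses the Screening endoscopy, as Operations Manual 3.16 says. No Mayo score is scheduled at Screening, so the literal reading leaves the rule nothing to act on before treatment. The Screening visit list also points sites to Section 8.2 for the diary calculation. This is a reasonable inference about intent, but no sentence extends the rule to Baseline, so sites and programmers could apply it differently.

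Exposure may also be small. The video must be read centrally before enrollment, and dysplasia in a Screening biopsy is exclusionary; both may lengthen the gap. This stands. No turnaround time is given, so the frequency cannot be derived in either direction.

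The examples use low daily scores, where the effect is largest. This too stands: daily SFS is capped at 3, so a subject already at 3 gains nothing on stool frequency. In the other direction, a sparse diary meeting only the minimum could give the affected days more weight than the 7-day figures show.

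Finally, a reader might infer that the comparison with historical placebo is biased in favor of ABBV-668 because no concurrent arm shares the inflation. The documents do not establish that. Protocol 4.2 says the external studies are aligned on endpoint definitions. If they scored Baseline in the same way, their placebo rates carry a similar inflation. How they handled these days is not stated.

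**Conclusion.** The gap in the wording is real and worth correcting. Read literally, the plan keeps at Baseline up to 4 of 7 diary days that it removes at Week 8. Under the assumed daily scores the shift is 0.57 to 1.71 points, enough to change an eligibility decision or a response call for an individual subject. The direction rests on these days scoring worse than ordinary days, which the exclusion itself presupposes.

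The direct effect is limited to entry and the two clinical-response secondary endpoints. Three stronger readings are not supported:

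- **The primary endpoint is compromised.** It is an ESS of 0 or 1 and uses no diary data. It is touched only through who is enrolled.
- **Clinical remission is materially affected.** It requires SFS of at most 1, RBS of 0 and ESS of at most 1 in absolute terms. The clause comparing SFS with Baseline matters only when clean Baseline SFS is below 1.
- **Baseline scores are in fact contaminated, or the gap always favors response.** The documents show that contamination can occur, not that it did, and at Week 10 the gap acts against response.

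**What to change.** In both subscore rules of Operations Manual 8.2, replace the opening condition with: *For any visit, including Baseline, whose diary window contains a day of bowel preparation, a day of endoscopy or either of the 2 days after endoscopy*. Keep the rule that earlier entries make up the 7 applicable days. State the same derivation in the SAP so that the analysis values for Baseline, Week 8, Week 10 and Week 16 follow one rule.

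The cost is one sentence per subscore, plus matching logic in the eligibility calculation and the analysis programs. No new data are needed: the diary is dispensed at Screening and already records medication used for endoscopy preparation. The downside is that a few borderline subjects may not qualify and some scores will rest on slightly earlier diary days. For subjects already enrolled, the entry decision stands, but the analysis Baseline can still be derived under the corrected rule.
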